- **Scar Assessment Scales:** The entire POSAS (both patient and observer scales) will be utilized (*see Appendix B*). Scar appearance will be assessed by the patient and by two independent observers (WRNMMC dermatologist subject matter expert investigator) who will be blinded to treatment provided at the wound site. Each scar (control and ReCell-treated sites, denoted on assessment forms as A Region and B Region due to “blinded” component) will be evaluated once by each observer. The evaluations will be made blind to each other. Findings will be documented in the eCRF.

In addition, the Vancouver Scar Scale (VSS) (*see Appendix C*) will be used at each of these visits. Using word descriptions, the VSS assesses four variables: scores pigmentation, vascularity, pliability and scar height/thickness. The four categories are given a score between 0 and 3 or 0 and 5, depending on the value, leading to a total score between 0 and 13 points. Evaluations of the control and ReCell-treated sites (denoted on assessment forms as A Region and B Region due to “blinded to treatment” component) will be performed utilizing this scale by the two independent observers (WRNMMC dermatologist subject matter expert investigator) who will be blinded to treatment provided at the wound site and will be recorded in the eCRF.

- **Functional Outcome Rating Questionnaire:** The Functional Outcome Rating Questionnaire consists of a 10-point visual analog scale (*see Appendix D*) used to

rate scar pain. Subjects will be asked to evaluate the amount of scar pain experienced at the control and ReCell-treated sites (denoted on assessment forms as A Region and B Region due to the subject being “blinded” to treatment). Findings will be documented in the eCRF.

- **Patient Satisfaction:** A 2-question (per study area) non-standardized Patient Satisfaction Questionnaire regarding treatment (denoted on assessment forms as A Region and B Region due to “blinded to treatment” component) (*see Appendix E*) will be completed by the subject and documented in the eCRF.

At Week 24 post-treatment:

- Radiographic imaging (anterior/posterior and lateral films) for assessment of presence/absence of heterotopic ossification.

The total duration of participant time commitment for each of the post-treatment study visits is approximately 1 hour.

Subject Discontinuation and/or Withdrawal

A subject may withdraw consent and discontinue participation in the study at any time and for any reason without penalty, if he/she wishes to do so. The investigator may also withdraw a subject if continuing participation is believed to be harmful to the subject’s well-being or in the event of protocol violations, non-compliance (i.e. loss to follow-up), the need to initiate care contraindicated to study procedures and/or requirements, pregnancy, serious inter-current illness and if the study is cancelled due to other administrative reasons and/or unanticipated circumstances by the Sponsor of this study or the FDA. Additionally, the subject’s participation may be stopped without their consent if the military mission requires it or if the individual loses his/her DoD healthcare beneficiary status.

If the subject’s participation is stopped, the investigator will notify the subject and provide reason for doing so in person, by mail, email and/or telephone.

In the event that the subject withdraws and/or is withdrawn from the study before the completion of the Week 24 post-treatment assessment, he/she will be asked to come to the clinic for a final assessment of safety evaluations. If a subject withdraws before study completion, the reason for discontinuation will be captured on the appropriate eCRF page. Additionally, any data collected up until the time of subject withdrawal will be included in the final study analysis. (*Please see section 5.5.7 for additional information pertaining to biological specimens/withdrawal*)

Subjects who are withdrawn will not be replaced if they have received study treatment.

Additional Information:

Patient and Observer Scar Assessment Scale (POSAS)

The standard and comprehensive Patient and Observer Scar Assessment Scale (POSAS) [Draaijers LJ, et al., 2004] will be employed in this study, as a standard tool for capturing both the subject’s and two independent observer’s assessment of the scar post-treatment

[Idriss N, 2009]. Although many methods of rating scars exist, little consensus exists to dictate which method is optimal [Fearmonti R, et al., 2010, Durani P, et al., 2009]. Objective measures may be useful for evaluating a particular characteristic (e.g. color or elasticity), but these do not satisfactorily convey overall, clinically-relevant information about the scar as a whole [Brusselaers N, et al., 2010].

The POSAS, consists of two multi-item numeric rating scales, an observer scale and a patient scale. The Observer Scale is devised with items based on literature review and the authors' clinical experience: 'vascularization', 'pigmentation', 'thickness', 'relief', 'pliability' and 'vascularization' rated on a 1 - 10-point numeric scale, with 'normal skin' and 'worst scar imaginable' used as end-anchor labels. The items on the Patient scale directly correspond to these except with regard to scar color. Individual items for both scales are summed with higher scores representing poorer scars and lower scores representing scars more closely resembling normal skin. Both scales have demonstrated acceptable internal consistency (Cronbach's alpha 0.76 (patient) and 0.69 (observer scale)), suggesting that individual items for each scale can be reliably summed to generate a total score. The POSAS has the added benefit of capturing the subjects' ratings for scar pain and itching and expands on the objective data captured in the VSS.

Vancouver Scar Scale (VSS)

The VSS is a quantitative objective scale which seeks to provide a standard for analyzing scar tissue. This assessment tool is widely used in clinical practice and research as it allows for a means to document changes in scar appearance. The scale is based on four values: pliability, height, vascularity and pigmentation. The four categories are given a score between 0 and 3 or 0 and 5, depending on the value, leading to a total score between 0 and 13 points. A low score indicates an appearance closer to normal skin.

Malfunction of ReCell Device

In the event of a malfunction occurrence of the ReCell device or any of the kit components, the "back-up" ReCell device dispensed by the investigational pharmacy will be utilized. In addition, if a ReCell kit or any of its components malfunctions and is replaced or results in an adverse event occurrence, the information will be documented in source documents and captured in the eCRF.

Procedure If Malfunctioning of Investigational Device Occurs:

If any device fails to operate, the failed ReCell device (kit) system will be returned to Avita Medical for evaluation via use of their established Return Material Authorization (RMA) process. Per manufacturer directives, the study site will notify manufacturer of need to return malfunctioning investigational device kit. They in turn will generate and send site an Investigational Device Return Form along with a return FedEx air bill to cover return shipment fees. The devices will be returned to the address below:

Return to:

Avita Medical
c/o Parker Hannifin Corp
ATTN: Customer Service
[name]
Ventura CA 93003

Histological methods:

Histological methods will be similar to those used in the Moiemmen and colleagues article [2006] who described histological analysis of punch biopsies taken from patients who had received INTEGRA™ MBWM treatment. That study identified four stages of tissue development after application of Integra. The first three phases, imbibition, fibroblast migration and neovascularization should be well established by the proposed study's first histological assessment four to six weeks after INTEGRA™ MBWM application (two weeks after ReCell treatment). Histological assessment of the proposed study will therefore focus on the last phase, remodeling and maturation, which begins four weeks after INTEGRA™ MBWM application, coinciding in time with our first scheduled punch biopsy. During this remodeling and maturation phase, fibroblasts imbue the matrix and fill the interstices with host collagen. Matrix collagen is progressively replaced by this new host collagen which appears as normal dermis. The neodermis is initially thicker than normal dermis, but becomes thinner and more pliable as it matures over a period of months. In the Moiemmen study, an autograft was applied to the wound four weeks after INTEGRA™ MBWM treatment. The autograft was seen to adhere to the surface of the neodermis during this final phase, and rete ridges were seen along the dermal-epidermal junction. Given the similarities between the proposed study and the methods used by Moiemmen and colleagues, we expect both ReCell-treated and control areas will show histological similarities to the results seen during the remodeling and maturation phase described in that study.

Punch biopsies of 3mm diameter will be obtained pre-skin graft from the INTEGRA™ MBWM treated wound site and adjacent normal skin and from ReCell and control treated sites at Weeks 2, 4 and 12 post ReCell treatment. The investigator will discuss the procedure with the subject in detail and will obtain a separate consent form as per standard of care. Samples will be analyzed to confirm the thickness of new tissue and assess the normality of structures present in the newly regenerated skin.

With the exception of the baseline INTEGRA™ MBWM treated wound site and adjacent normal skin punch biopsies, the procedure will take place in a private room within the Orthopaedic Surgery, General Surgery Service and/or Plastic Surgery Service clinic at WRNMMC. Utilizing sterile technique, the site will be prepped and draped as per standard of care. Approximately 3-5cc's of 1% lidocaine (with epinephrine) solution will be instilled as a local analgesic to the treated wound area (Note: No local analgesic will be used for pre-STSG sample as subject will be anesthetized for surgical procedure). The specimen will be obtained by using a standard punch biopsy instrument consisting of a circular blade, which is rotated down through the epidermis and dermis, and into the subcutaneous fat. The PI and/or AI, who are surgeons, will collect a 3mm diameter cylindrical core of tissue sample from a centralized region of both the control and ReCell treated wound sites.

All tissue samples will be coded and labeled with the subjects' 3-digit ID number, date and time of harvest. Tissue samples will be cut in half with a sterile scalpel; one half of the sample will be preserved in 10% formalin by a member of the study team then delivered to Annapath Inc via courier pick-up for tissue processing, embedding (paraffin

blocks), microtomy and slide preparation as per Annapath, Inc Technical Guidelines and Annapath, Inc Procedure Protocol (*see Appendix F and Appendix G*). The other half of tissue sample will be flash frozen with liquid nitrogen then stored in a -80° freezer with alarm system located within the Department of Orthopaedics Biomedical Lab Room 2010, Building 19 (America).

Following the methods detailed by Moimen and colleagues, hematoxylin and eosin stains will be used to detect blood cells and adnexal structures, vimentin stain will be used to detect esenchyme-derived cellular elements including fibroblasts, and S100 will be used to stain neuroectodermal tissue. Vascularization will be assessed by immunohistochemical analysis using antisera to endothelial cell markers CD31 and CD34. In addition, Verhoeff-Van Gieson (VVG) stain will be used for identifying elastic fibers and Masson's Trichrome stain will be used for the detection of collagen fibers.

Sections will also be assessed visually with an electron microscope to aid morphological evaluation of structures by WRNMMC's dermatopathologist. The dermatopathologist will provide a written report summarizing their findings. This information will be captured in the eCRF and entered into the database.

The Research Coordinator will call the subject within 72 hours after the biopsy procedure to obtain a subject self-report assessment of signs/symptoms of an adverse event post-biopsy (bleeding or signs/symptoms of infection) as standard of care follow-up to a surgical procedure.

Digital Photography Method:

When followed by different physicians, a uniform assessment of changes in the healing process needs to be established. Therefore, to facilitate uniform assessment/rating and improve reproducibility of the results, digital photography for clinical evaluation and follow-up of subjects will be utilized to minimize variations between different assessors. The definition for successful healing of the target wound via digital photography will be defined as: The target wound will be deemed as "successful healing" when 95% or greater re-epithelialization is noted upon visualization of the treated wound within the photograph taken.

In this study, clinical photographs will be obtained through the Biomedical Photography Department located at WRNMMC.

The Biomedical Photography Department is responsible for all medical photography taken and stored at WRNMMC. Photos taken through Biomedical Photography Department are obtained as standard of care and are stored and maintained as a part of the patient's medical record following institutional policies. Digital photographs will be taken in ambient light with a consistent background and distance between camera and subject. Physical features identifying the subject (i.e. tattoo or birthmark), if present, will be hidden in photographs.

A photograph of the wound will be taken pre-treatment and then serial photographs will be taken of the ReCell donor site and at the treated and control wound sites at each follow-up visit. Additional photographs may be obtained outside of the

stated study time points for evaluation purposes if medically indicated (i.e. incomplete healing and/or AE occurrence).

A copy of the digital photographs will be obtained from the Biomedical Photography Department to be placed in the study files. Photographs will be coded by using the unique 3-digit study ID number and labeled each with the date the photograph was obtained, the corresponding visit (e.g. pre-treatment and/or post-treatment week) and site location (e.g. treatment site (ReCell or control) or donor site (ReCell donor site or STSG) then placed on a disc to be stored with the main study database at completion of the study.

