A Pharmacy Manual will be provided by the Sponsor to maintain records of investigational device disposition. The Research Pharmacist will follow the procedures in this manual for maintaining adequate records for documentation purposes of shipment and receipt of the investigational device, device dispensing records and maintaining device accountability log and final disposition of the investigational devices to include return of unused devices.

The ReCell device will be administered only to those subjects enrolled in the clinical study and under investigator or designee's supervision (as noted on the Enrollment/Randomization Log and Delegation of Responsibility Log maintained in the study regulatory files).

Re-verification of subject meeting all inclusion and exclusion criteria will be confirmed by the investigator before obtaining the ReCell device kit from the investigational pharmacy on the day of surgery.

Treatments with the ReCell device will be staggered for the initial three subjects. A treatment pause period of 1 week (5-7 days) will be implemented for the first and second subject, as well as the second and third subject within this study.

On the day of surgery, a member of the study team will pick up 2 kits; one will be dispensed for use and the other will be obtained for the purpose of having "on-hand" in the event of a device malfunction while in the operating room. The investigational pharmacist will record dispensing of both device kits. One kit will be denoted as

“intended for use” and the second kit will be denoted as the “back-up device” in the device accountability log. At the end of surgery, the second device deemed as the “back up device” will be returned to the investigational pharmacy by the study coordinator and logged back in on the device accountability log to be dispensed for future use with the next subject enrolled. Stringent record keeping of this process will be maintained for device accountability.

Anesthesia procedures will follow the same clinical standards as all operative procedures performed at WRNMMC. Subjects will be maintained NPO after midnight the morning of surgery. With the ReCell treatment, the subject will be given general anesthesia during the entire procedure. No data will be collected for the anesthetic regimen provided.

Surgical Procedure and Methods:

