Subjects will be anesthetized and the wound will be prepared according to hospital standard of care practices. It is anticipated that the total surgical time will be up to 3 hours. The operative procedure will be performed by the PI and/or the Co-PI in the operating room at WRNMMC. The INTEGRA™ MBWM treated wound will be sectioned into two **similarly sized** study regions up to 320cm² each, the upper limit of application area for one ReCell kit. The surgeon will label these two regions “A” and “B” with a surgical pen. A pre-generated randomization envelope will then be opened to determine which area will be the control area and which area will be treated with ReCell. Any wound area outside the study regions will be treated according to standard of care.

In this study, serial histology assessments of the wound site will be made. Baseline punch biopsies of 3 mm diameter tissue samples from the INTEGRA™ MBWM treated wound site and adjacent normal skin will be obtained in the operating room prior to start of the surgical procedure. This baseline histological analysis will examine the vasculogenesis and cytology of the regenerate before ReCell treatment. The biopsy procedure will be recorded in the eCRF.

A digital photograph will be taken of the control and ReCell sites (“A” region and “B” region) and noted on the eCRF. Next, the wound bed will be gently scrubbed and “prepared” then the thin silicone layer is removed, the wound bed will be prepped and prepared again for receipt of proposed STSG or STSG in conjunction with ReCell regenerative skin treatment system.

Harvesting of autograft will be the same thickness for both control and investigational site; at a depth of 0.012 inch to 0.016 inch which is alignment with standard of care practice. Donor tissue for the STSG for the ReCell treatment area may be harvested from the same area as for the control STSG or separate area. To assess healing of the donor sites for ReCell, the site has to be at a discrete location, but can be collocated, i.e. same thigh, but different area.

A digital photograph will be taken of donor sites following tissue removal and will be noted in the eCRF. These and all subsequent photographs at each study visit will be taken in ambient light, with a consistent background and distance between camera and subject.

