placement of the primary dressing, a secondary dressing, Xeroform™ Petrolatum Gauze (Covidien, USA) will be applied to keep wounds moist then area will be wrapped with bulk dressing (e.g. gauze) to protect the wound surface, with or without an adhesive retention dressing as clinically indicated. The primary and secondary dressings should remain in situ for a minimum of 6 to 8 days and are not to be manipulated until the first post-operative visit unless medically necessary.

The donor area will be dressed in the following manner: The primary dressing will be Xeroform™ Petrolatum Gauze (Covidien, USA). The area will then be wrapped with bulk dressing (e.g. gauze) plus or minus a compressive wrap (ace-wrap) based on the area of harvest (extremity vs torso). The donor area bulk dressing will be removed at 48 hours. The primary dressing (Xeroform™ Petrolatum Gauze) will remain in place and be gradually peeled off over several days.

The primary dressing can be trimmed and removed as the Telfa™ Clear lifts from the wound bed. Under no circumstances will the primary dressing be forcibly removed; the Telfa™ Clear should be allowed to fall off on its own accord. If the Telfa™ Clear dressing hasn't fallen off in 3 weeks, only at this time point can it be moisten to peel off. It is essential that any dressing not easily removed be soaked in aqueous or oil-based solutions to prevent trauma upon removal. Once the primary dressing has been removed, a dressing of the investigator's choice will be applied to protect the wound surface, with or without an adhesive retention dressing as clinically indicated. All dressing regimens, dressing changes and dressing types will be recorded on the eCRF. Once the wounds are determined to be healed, therapy will be applied that is consistent with the standard of care at the clinical site.

Any dressing used other than Telfa™ Clear as primary dressing and Xeroform™ Petrolatum Gauze as secondary dressing at the treatment site areas prior to wound healing will be considered a protocol deviation.

Negative pressure wound therapy (NPWT) (i.e. wound vac) will not be reapplied after treatment with ReCell as this may compromise the treated area by removing the applied cells.

Post-Operative Care:

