Following surgery, subjects will be transferred to the Post Anesthesia Care Unit (PACU) and then to the In-Patient ward. Post-Operative recovery in terms of hospitalization and length of stay will be as per standard of care for this type of procedure.

It has been identified from previous use, the loss of formed skin at the ReCell site appears to be primarily associated with secondary trauma due to inadvertent inadequate care and/or protection of the newly epithelialized area. As a corrective measure, the wound will be appropriately protected while the skin is maturing. These measures include use of appropriate protective dressings after initial wound closure to give the epithelium adequate time to mature and cornify, ensuring the primary dressing removal is atraumatic and not before post-treatment Day 6 and avoidance of potentially damaging cleansing regimens and cytotoxic creams (i.e., silver sulfadiazine). Additionally, for the duration of their care, subjects will be informed on the following post-treatment ReCell site care

guidelines recommended by the manufacturer:

- Prevent the treated area from getting wet while the wound is still open
- Refrain from strenuous activity
- Protect the healed area; don't bump, wear loose clothing over treated area
- Once the area has healed, massage and keep area moisturized (using a gentle moisturizer) at least twice a day
- Avoid direct sun exposure at least 4 weeks following treatment and use sunscreen

Post-Treatment Study Visits

Subjects will be re-evaluated by the Orthopaedic Surgery Service, General Surgery Service and/or Plastic Surgery Service clinic at WRNMMC or on the in-patient wards. At all post-treatment study visits (Week 1 \pm 3 days, Weeks 2, 3, 4, 6 \pm 2 days, Weeks 12 and 24 \pm 14 days post-treatment), the PI and/or AI will perform the following assessments as outlined below:

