Working from source documents and the data collection forms, the Research Coordinator will update the Medrio data management system within one week after each scheduled study visit for the subject.

All data collection activities will be monitored by IMARC Research, Inc.; qualified monitors, based on training and experience, will be assigned to this study as per Clinical Monitoring Plan (*see Appendix I*). Periodic onsite monitoring visits will be made to WRNMMC by the IMARC Research, Inc. clinical trial monitors to inspect the conduct of the study to determine if it is being executed according to the protocol and report their findings to the Sponsor. The monitors will assure that data is accurately captured on the eCRF and in agreement with source documentation; verify that investigational product is properly stored and accounted for, verify that subjects' consent for study participation has been properly obtained and documented, confirm that research subjects entered into the study meet inclusion and exclusion criteria, and assure that all essential documentation required by Good Clinical Practice (GCP) guidelines are appropriately filed.

In collaboration with Glaser Consultants, CIRM will perform all statistical analysis of intermittent data and upon completion of all subject visits.

The Investigator is responsible for maintaining any source documentation related to the study, including digital photographs of the donor sites and wound site treated with the investigational product, clinical laboratory data, radiographic imaging (x-ray results) for assessment of heterotopic ossification, histology analysis, informed consent forms and device accountability records.

a. Method of Collection from Study Participants:

Please refer to above Section 5.5.4

Please refer to CRF's included with this submission

The method for collection of clinical data from study participants by members of the study site personnel will be derived from interviews and assessments performed by the study investigator and/or coordinator during study visits. Study materials, information, photographs, radiographic imaging (x-ray results) for assessment of heterotopic ossification and biopsy samples obtained for the purpose of this clinical trial will be coded with the subjects assigned 3-digit study ID number. Listed below is data that will be collected at the following time points:

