5.5.6 Collection of Human Biological Specimens

Human biological samples will be collected for this study; blood and tissue.

Bloodwork: A blood sample (15 mls) will be drawn for hematological analysis including a CBC with differential panel, coagulation studies to include prothrombin time (PT) and international normalized ratio (INR) and comprehensive metabolic panel (CMP) at screening pre-treatment and at Week 1 post-ReCell treatment, which is consistent with standard of care practices. Samples will be labeled and processed by WRNMMC laboratory medicine per institutional policy. Therefore, these samples will be labeled with subject identifiers. Additional laboratory testing will be performed only as clinically indicated. Any leftover blood from sample will be discarded per WRNMMC policy.

Punch biopsy: A tissue sample size of 3mm diameter will be obtained pre-treatment (baseline) from the INTEGRA™ MBWM treated wound site and adjacent normal skin and from the control and ReCell treated sites at at Week 2, 4 and 12 post-ReCell treatment. All tissue samples will be coded and labeled with the subject's 3-digit ID number, date and time of harvest. Tissue samples will be cut in half with a sterile scalpel; one half of the sample will be preserved in 10% formalin by a member

of the study team then delivered to Annapath Inc. via courier pick-up for tissue processing, embedding (paraffin blocks), microtomy and slide preparation as per Annapath, Inc Technical Guidelines and Annapath, Inc Procedure Protocol (see Appendix F and Appendix G). The other half of tissue sample will be flash frozen with liquid nitrogen then stored in a -80° freezer with alarm system located within the Department of Orthopaedics Biomedical Lab Room 2010, Building 19 (America).

As previously mentioned, one half of the tissue sample obtained for histology analysis will be frozen. The rationale for doing this is to preserve the ability to return to the frozen sample, if need be, in the event we do not get immunohistochemical analysis staining needed from the formalin fixed slides. Oftentimes formalin fixed tissue does not perform as expected therefore, necessitating the need to freeze part of the sample to preserve options. The frozen samples will only be stored for evaluation within the period of funding for this research project then destroyed as per institutional policy standards.

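### The 5-7 day pause between the first three subjects has no release condition, so it can end before the previous subject's Week 1 examination and bloods

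*Combined protocol and SAP*

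**What the plan says.** The only supplied text on staggering is one short paragraph in 5.5.4, before the surgical procedure: "A treatment pause period of 1 week (5-7 days) will be implemented for the first and second subject". The same pause applies between the second and third subjects. No purpose is given, and no examination, laboratory result, reviewer or decision is attached.

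Other parts of the plan fix what can be known by the time the pause ends:

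- **Week 1 visit.** 5.5.4 (Post-Treatment Study Visits) and the schedule of procedures allow ±3 days. This is the first scheduled investigator assessment of the treated wound, the donor sites, infection and a response to trypsin.
- **Bloods.** 5.5.6 schedules them "at screening pre-treatment and at Week 1 post-ReCell treatment"; any others are drawn only if clinically indicated.
- **Treated-wound dressings.** Under 5.5.4 (Dressings), the rule for both layers over the treated wound is that they "should remain in situ for a minimum of 6 to 8 days and are not to be manipulated until the first post-operative visit"; a medical need is the only exception. Post-Operative Care adds the aim of "ensuring the primary dressing removal is atraumatic and not before post-treatment Day 6".
- **Donor site.** "The donor area bulk dressing will be removed at 48 hours".
- **Oversight.** 6.3 plans no interim analysis, no stopping rules and no DSMB. The IRB, the medical research monitor and the PI review safety concerns as they arise. 6.4 sets 24-hour reporting and lets the monitor stop the study.

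**The concern.** A stagger is usually worth its delay because something is learned from one subject before the next is exposed. Here it is the only pre-planned hold on exposure in the supplied text, and it is defined by elapsed days alone. A site could follow every supplied instruction, treat subject 2 on Day 5-7, and first examine subject 1 at a scheduled visit on Day 8-10.

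Section 4.2 cites over 5,000 ReCell procedures but reports no preliminary data for this indication. Safety and tolerability are the primary outcomes (5.7.1). Section 6.2 puts partial graft loss at 10% or more and total graft loss at 5% to under 10%. Early signs of either would be looked for at the first wound examination. Delayed healing (judged at Week 6) and follow-up films for heterotopic ossification (Week 24) come too late to inform any pause of this length, so what is at stake is limited to the Week 1 findings.

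**Working it through.** The pause has no derivation to reproduce, so the check is a comparison of permitted days. Count the day of treatment as Day 0.

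**Inputs**
- Pause end, P: Day 5, 6 or 7 (5.5.4).
- Week 1 visit, V: Day 7 ± 3, so Day 4 to Day 10, which is 10 − 4 + 1 = 7 permitted days (5.5.4 and schedule of procedures).
- Earliest planned primary dressing removal: Day 6 (5.5.4, Post-Operative Care).

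**Visit day against pause end**

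| Pause ends | Visit earlier (V < P) | Same day (V = P) | Visit later (V > P) | Longest lag, 10 − P |
|---|---|---|---|---|
| Day 5 | 1 of 7 | 1 of 7 | 5 of 7 | 5 days |
| Day 6 | 2 of 7 | 1 of 7 | 4 of 7 | 4 days |
| Day 7 | 3 of 7 | 1 of 7 | 3 of 7 | 3 days |

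Summed over the 3 × 7 = 21 permitted pairs, the visit is later in 5 + 4 + 3 = 12, on the same day in 3, and earlier in 6. These count permitted schedules. They are not probabilities.

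**Adding the dressing rule.** A 5-day pause ends before Day 6. If the 8-day end of the 6-8 day dressing minimum is used, all three pause lengths end before it. Of the 6 pairs with the visit earlier, the visit falls on Day 4 (P = 5), Day 4 or 5 (P = 6), or Day 4, 5 or 6 (P = 7). Five of those six visits are therefore before Day 6, when the primary dressing is still meant to be in place. An early Week 1 visit does not by itself provide a planned look at the graft.

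**Does anything else in the text make the next treatment conditional?**
- Inpatient recovery (5.5.4): follows standard of care, and the treated-wound dressings stay undisturbed unless there is a medical need.
- Donor bulk dressing removal at 48 hours: concerns the donor site only.
- Call within 72 hours of a biopsy: asks about bleeding and infection by self-report. The baseline biopsies are taken in the operating room, so the call can fall inside the pause.
- Instruction to report significant AEs (6.2), review of safety concerns (6.3) and 24-hour reporting (6.4): all triggered by an event.
- Monitor's power to stop the study (6.4): a discretionary act, with no link to the pause.

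Each lowers the chance that a problem is missed. None is a condition for treating the next subject.

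**The case against.** The strongest reply is that the stagger's purpose is unstated. If it is aimed at acute perioperative or device problems, 5-7 days with inpatient care and 24-hour reporting largely serves it. This stands, and it limits the point to an improvement.

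Second, this is one site. Only the PI and/or Co-PI operate and apply the product, and the PI and/or AI perform the follow-up visits. The team treating subject 2 will probably know how subject 1 is doing, and the monitor can stop the study. This also stands as mitigation, though informal knowledge does not replace an examination that has not yet taken place.

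Third, Week 1 may show less than hoped. The Telfa Clear must never be forced off and may be moistened for peeling only if still on at 3 weeks, so the graft may be partly covered. Abnormal bloods are expected in this trauma population. Both are fair. They limit what a Week 1 condition can deliver, but this is still the first information the plan schedules.

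A reader might infer that the next subject would often be treated before the Week 1 visit, or that a safety failure has been shown. The documents support neither. They give no accrual rate or distribution of visit days, so the day counts cannot become a frequency, and a site that pauses 7 days and sees the subject on Day 6 has no overlap. Nor can one infer that no review step exists anywhere: the Data Management Plan, Clinical Monitoring Plan and Pharmacy Manual are named but their contents are not supplied.

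**Conclusion.** The point holds as a cheap improvement, with moderate confidence. As written, each permitted pause length can end before the previous subject's Week 1 visit: 5, 4 or 3 of the 7 permitted visit days are later for pauses of 5, 6 or 7 days, by at most 5, 4 or 3 days. A 5-day pause also ends before the earliest planned primary dressing removal. At most two intervals are affected.

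This rests on counting Week 1 as Day 7 after treatment, on reading the pause as running from one treatment to the next, and on the supplied text alone. It matters only if the stagger is meant to let the first look at the graft and the post-treatment bloods inform the next exposure; the plan does not say whether it is.

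**What to change.** Amend the staggering paragraph in 5.5.4. Keep 5-7 days as the minimum, and treat subjects 2 and 3 only after the previous subject's Week 1 visit meets these conditions:

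- For subjects 1 and 2 the visit is required, not merely aimed for, on Day 6-8. This lies inside the existing window and matches the 6-8 day dressing minimum. Without it, a Day 4 visit with dressings untouched would satisfy the rule.
- The wound has been inspected as far as the dressing rules allow, with no forced removal of the Telfa Clear, and donor sites and AEs have been assessed.
- Blood results are back.
- The PI has reviewed the findings from source documents, because 5.5.5 allows eCRF entry "within one week after each scheduled study visit for the subject". Any safety concern goes to the medical research monitor under 6.3 before proceeding. This adds no routine review duty for the monitor.

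A sentence stating the stagger's purpose would help. If an appendix already holds such a condition, a cross-reference in 5.5.4 is enough.

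**Cost.** With the visit on Day 8, each interval lengthens by 8 − 7 = 1 to 8 − 5 = 3 days, or 2 to 6 days over two intervals, plus time for blood results and review. With the visit on Day 6 the addition is 6 − 5 = 1 day after a 5-day pause and none after a 6- or 7-day pause, again before results and review. A subject with a graft-ready wound may have to wait those days. The visit and bloods are already scheduled. The change needs a protocol amendment with prior IRB approval. A fixed pause would have to exceed 10 days to give the same ordering under the current window, which is a longer delay.
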